4.2. Overall Study Duration

The study begins when the first participant signs the ICF. Treatment will continue for an individual participant as long as the regimen is tolerated and the participant does not meet discontinuation criteria. The end of the study is defined as the date of the last visit/last contact of the last participant in the study.

4.3. Study Termination

The investigator retains the right to terminate study participation at any time, according to the terms specified in the study contract. The investigator/head of study site (Japan) is to notify the IRB/IEC of the study's completion or early termination in writing, send a copy of the notification to the sponsor or sponsor's designee, and retain 1 copy for the site study regulatory file.

The sponsor may terminate the study electively if, for example, required by regulatory decision or upon advice of the DMC. If the study is terminated prematurely, the sponsor will notify the investigators/head of study site (Japan), the IRBs and IECs, and the regulatory bodies of the decision and reason for termination of the study. The DMC may recommend termination of the study if warranted, as described in Sections 5.6 and 10.5. For Japan, the head of the study site will notify the investigators and IRBs of the decision and reason for termination of the study.

5. STUDY POPULATION

Male or female participants aged 18 years or older (19 years or older in South Korea) who have been diagnosed with PMF or secondary MF (PPV-MF or PET-MF), who have intermediate- or high-risk disease according to DIPSS, who are naive to both prior JAK and prior PI3K therapy, and for whom treatment of MF is indicated may enroll.

Deviations from eligibility criteria are not allowed because they can potentially jeopardize the scientific integrity of the study, regulatory acceptability, and/or participant safety. Therefore, adherence to the criteria as specified in the Protocol is essential. Prospective approval of Protocol deviations to recruitment and enrollment criteria, also known as Protocol waivers or exemptions, are not permitted.

5.1. Inclusion Criteria

Participants are eligible to be included in the study only if all of the following criteria apply:

1. Men and women aged 18 years or older.
 Note: For South Korea, men and women aged 19 years or older.
2. Diagnosis of PMF, PPV-MF, or PET-MF.
3. DIPSS risk category of intermediate-1, intermediate-2, or high (see [Table 8](#) and [Table 9](#)).

Table 8: Risk Categories According to DIPSS

Number of Risk Factor Points Present	Risk Category
0	Low
1-2	Intermediate-1
3-4	Intermediate-2
5-6	High

Table 9: Risk Factors and Point Assignments for DIPSS

Risk Factor	Points Assigned
Age older than 65 years	1
Presence of constitutional symptoms	1
Hemoglobin < 10 g/dL	2
WBC count > 25 × 10 ⁹ /L	1
Presence of peripheral blood blasts (lab value ≥ 1%)	1

4. Evidence of need for treatment for MF (both a and b must be satisfied):
 - a. Palpable spleen of ≥ 5 cm below the left costal margin on physical examination at the screening visit
 - b. Active symptoms of MF at the screening visit, as demonstrated by the presence of a TSS of ≥ 10 using the Screening Symptom Form (see [Appendix C](#)).
5. Participants with an ECOG performance status score of 0, 1, or 2 (see [Appendix D](#)).
6. Screening bone marrow biopsy specimen and pathology report(s) available that was obtained within the prior 2 months or willingness to undergo a bone marrow biopsy at screening/baseline; willingness to undergo bone marrow biopsy at Week 24 and every 24 weeks thereafter. Screening/baseline biopsy specimen must show diagnosis of MF.
7. Life expectancy of at least 24 weeks.
8. Willingness to avoid pregnancy or fathering children based on the criteria below.
 - a. Female participants without childbearing potential (ie, surgically sterile with a hysterectomy and/or bilateral oophorectomy OR ≥ 12 months of amenorrhea and at least 50 years of age) are eligible.
 - b. Female participants with childbearing potential must have a negative serum pregnancy test at screening and negative urine pregnancy test before the first dose on Day 1 and must agree to take appropriate precautions to avoid pregnancy (with at least 99% certainty) from screening through safety follow-up. Permitted methods that are at least 99% effective in preventing pregnancy (see [Appendix A](#)) should be communicated to the participant and their understanding confirmed.
 - c. Male participants with childbearing potential must agree to take appropriate precautions to avoid fathering children (with at least 99% certainty) from screening through 93 days after the last dose of study drug and must refrain from donating sperm during this period. Permitted methods that are at least 99% effective in preventing pregnancy (see [Appendix A](#)) should be communicated to the participant and their understanding confirmed.

5.2. Exclusion Criteria

Participants are excluded from the study if any of the following criteria apply:

1. Prior use of any JAK inhibitor.
2. Prior therapy with any drug that inhibits PI3K (examples of drugs targeting this pathway include but are not limited to INCB040093, idelalisib, duvelisib, buparlisib, copanlisib, and umbralisib).
3. Use of experimental drug therapy for MF or any other standard drug (except hydroxyurea) used for MF or another indication within 3 months of starting study drug and/or lack of recovery from all toxicities from previous therapy to \leq Grade 1. Hydroxyurea used for MF or another indication must be discontinued 3 weeks prior to starting study drugs (Day 1).
4. Inability to swallow food or any condition of the upper gastrointestinal tract that precludes administration of oral medications.

5. Recent history of inadequate bone marrow reserve; examples include but are not limited to the following:
 - a. Platelet count $< 50 \times 10^9/L$ in the 4 weeks before screening or at the screening laboratory assessment; or platelet transfusion(s) within 8 weeks before screening.
 - b. Absolute neutrophil count $< 0.5 \times 10^9/L$ in the 4 weeks before screening or at the screening laboratory assessment.
 - c. Peripheral blood blast count of $\geq 10\%$ at the screening hematology assessment.
6. Inadequate liver function at screening visit, as demonstrated by the following:
 - a. Total bilirubin $> 2.0 \times ULN$. Note: if total bilirubin is $> 2.0 \times ULN$, the participant may enroll if the direct bilirubin is $< 2.0 \times ULN$.
 - b. ALT or AST $> 2.5 \times ULN$.
7. Inadequate renal function at screening, as demonstrated by creatinine clearance ≤ 50 mL/min estimated based on Cockcroft-Gault formula. The cutoffs for mild, moderate, and severe renal insufficiency based on the Cockcroft-Gault formula are 60 to 90 mL/min, 30 to 59 mL/min, and 0 to 29 mL/min, respectively. If the investigator prefers, he/she may use measured creatinine clearance instead of estimated.
8. Active bacterial, fungal, parasitic, or viral infection that requires therapy. Participants with acute infections requiring treatment should delay screening/enrollment until the course of therapy has been completed and the event is considered resolved. Prophylactic antibiotics or antivirals will be permitted.
9. Active HBV or HCV infection that requires treatment or at risk for HBV reactivation. Hepatitis B virus DNA and HCV RNA must be undetectable upon testing. At risk for HBV reactivation is defined as hepatitis B surface antigen positive or anti-hepatitis B core antibody positive. Cytomegalovirus must be undetectable by polymerase chain reaction.
10. Known HIV infection.
11. Uncontrolled, severe, or unstable cardiac disease that in the investigator's opinion may jeopardize the safety of the participant or compliance with the Protocol.
12. Active invasive malignancy over the previous 2 years except treated basal or squamous carcinomas of the skin, completely resected intraepithelial carcinoma of the cervix, and completely resected papillary thyroid and follicular thyroid cancers. Participants with malignancies with indolent behavior such as prostate cancer treated with radiation or surgery may be enrolled as long as they have a reasonable expectation to have been cured with the treatment modality received.
13. Splenic irradiation within 6 months before receiving the first dose of study drug.
14. Concurrent use of any prohibited medications (see Section 6.8.5 for specific prohibited medications and the associated timeframe over which they are prohibited).
15. Active alcohol or drug addiction that would interfere with the ability to comply with the study requirements.

16. Use of any potent CYP3A4 inhibitors or inducers within 14 days or 5 half-lives (whichever is longer) before the first dose of study drug or anticipated during the study.
17. Inadequate recovery from toxicity and/or complications from a major surgery before starting therapy.
18. Currently breastfeeding or pregnant.
19. Any condition that would, in the investigator's judgment, interfere with full participation in the study, including administration of study drug and attending required study visits; pose a significant risk to the participant; or interfere with interpretation of study data.
20. Inability to comprehend or unwilling to sign the ICF.
21. History of Grade 3 or 4 irAEs from prior immunotherapy.
 - a. Any irAEs of Grade 1 or 2 must be resolved before receiving the first dose of study drug.
22. Receipt of any live vaccine within 30 days of the first dose of study drug.
23. Unwillingness to receive RBC transfusions to treat low hemoglobin levels.
24. Immediately eligible for allogeneic stem cell transplantation.
25. Known hypersensitivity or severe reaction to pascalisib or ruxolitinib or excipients of pascalisib/matching placebo or ruxolitinib formulations.

5.3. Lifestyle Considerations

No restrictions are required.

5.4. Screen Failures

Screen failures are defined as participants who consent to participate in the clinical study but are not subsequently randomly assigned to study treatment/entered in the study.

Results from the screening visit evaluations will be reviewed to confirm participant eligibility before enrollment/randomization or the administration of study drug. Tests with results that fail eligibility requirements may be repeated once during screening if the investigator believes the results to be in error. For screening assessments that are repeated, the most recent available result before randomization/treatment assignment will be used to determine participant eligibility.

Additionally, a participant who fails screening may repeat the screening process 1 time if the investigator believes that there has been a change in eligibility status (eg, after recovery from an infection). Participants who rescreen must reconsent and be assigned a new participant number.

5.5. Replacement of Participants

No participants will be replaced at any time during this study.

5.6. Data Monitoring Committee

Preplanned analyses of safety and efficacy will be provided to an independent DMC as specified in the DMC charter. The process by which the DMC will review data and make recommendations and decisions will be documented in the DMC charter. The external DMC will also conduct the interim analyses (see Section 10.5).

6. STUDY TREATMENT

6.1. Study Treatments Administered

Table 10 presents the study treatment information.

Table 10: Study Treatment Information

	Study Treatment 1	Study Treatment 2	Reference (Background) Treatment
Study treatment name:	Parsaclisib	Placebo	Ruxolitinib
Dosage formulation:	Tablets	Tablets	Tablets
Starting dose:	5 mg QD without regard to food	5 mg QD without regard to food	5 mg BID if baseline platelet count is 50 to $< 100 \times 10^9/L$ inclusive ^a ; 15 mg BID if baseline platelet count is $\geq 100 \times 10^9/L$; dosing is without regard to food
Start day for dosing	Day 1	Day 1	Day 1
Time of dosing	Morning	Morning	Morning/evening, approximately 12 hours apart
Unit dose strength(s)/ dosage level(s):	5 mg tablets, 2.5 mg tablets, 1.0 mg tablets	5 mg tablets, 2.5 mg tablets, 1.0 mg tablets	5 mg tablets 15 mg tablets (in some countries)
Route, frequency of administration:	Oral, QD	Oral, QD	Oral, BID
Packaging and labeling:	Parsaclisib will be provided in bottles. Each bottle will be labeled as required per country requirement.	Placebo will be provided in bottles. Each bottle will be labeled as required per country requirement.	Ruxolitinib will be provided in bottles, blister packs, or other packaging and will be labeled as required per country requirement.
Storage Conditions	Refer to the Pharmacy Manual.	Refer to the Pharmacy Manual.	Per labeling instructions.
Status of treatment in participating countries:	Experimental	Not applicable	Approved

^a If a baseline platelet count has decreased to $< 50 \times 10^9/L$ at baseline, the platelet count at screening should be used to determine the starting dose of ruxolitinib.

Note there is no order for the morning doses of parasclisib/matching placebo and ruxolitinib. They may be taken together or in any order in the morning.

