Treatment Groups and Duration:

This is a Phase 3, randomized, double-blind study of the combination of the PI3K δ inhibitor piasclisib or matching placebo and the JAK1/2 inhibitor ruxolitinib in participants with primary MF or secondary MF (PPV-MF or PET-MF) with DIPSS risk category of intermediate or high. After participants have been determined to meet all criteria, they will be randomized to 1 of 2 treatment groups and will receive piasclisib or matching placebo at a dose of 5 mg once daily beginning on Day 1. Participants will also receive ruxolitinib, at doses determined by baseline platelet count, beginning on Day 1. Both piasclisib/matching placebo and ruxolitinib dosing will continue for the duration of participation in the study.

Figure 1 presents the study design schema, and Table 3, Table 4, and Table 5 show the SoA for study site visit assessments, post-crossover assessments, and laboratory assessments, respectively. Adherence to the study design requirements, including those specified in the SoA, is essential and required for study conduct.

Figure 1: Study Design Schema

[figure not shown]

Table 3: Schedule of Activities for Randomized Participants in Group A, in Group B, and After Crossover

Visit Day (Range)	Screening (Day -35 to Day -8)	Baseline (Day -7 to Day -1)	Day 1	End of Week 2 ± 3 Days	End of Weeks 4, 8, 16, and 20 ± 5 Days	End of Weeks 12 and 24 ± 5 Days	Extension Visits (Every 12 Weeks After Week 24) ± 7 Days	EOT or Early Termination Visit ± 5 Days	Safety Follow-Up (End of Treatment + 30-35 Days)	Survival Follow-Up (Every 12 Weeks ± 2 Weeks)	Notes
Administrative procedures											
Informed consent	X										
Contact IXRS	X		X		X	X	X	X			
Inclusion/exclusion criteria	X	X	X								
General and disease medical history	X										
Prior/concomitant medications	X	X	X	X	X	X	X	X	X		
Dispense parasclisib/matching placebo and ruxolitinib			X		X	X	X				
Administer parasclisib/matching placebo and ruxolitinib at clinic visit			X	X	X	X					
Distribute reminder cards and dosing diary where applicable	X	X	X	X	X	X	X	X			
Collect study drug and review dosing diary					X	X	X	X			
Assess drug compliance					X	X	X	X			
Transfusion history status	X										Record of transfusions must include at least 12 weeks prior to screening visit.

Table 3: Schedule of Activities for Randomized Participants in Group A, in Group B, and After Crossover (Continued)

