2.6.2. Risks of Ruxolitinib

2.6.2.1. Potential Risks of Ruxolitinib

The primary clinical risks with ruxolitinib treatment are the potential sequelae of decreased hematopoietic proliferation attributable to the inhibition of growth factor pathways associated with JAK inhibition. Dose-dependent, reversible thrombocytopenia has been observed in studies of participants with MF. Anemia and, less frequently, neutropenia have also been observed in studies in participants with MF. In healthy volunteers, participants with rheumatoid arthritis, and participants with hormone-refractory prostate cancer with greater bone marrow reserve, the effects on hematopoietic proliferation appear to be less pronounced. Increased rates of infection and anemia are potential risks of myelosuppression, and there are multiple sequelae of anemia, including the burden and risks of transfusion. Serious bacterial, mycobacterial, fungal, viral, and other opportunistic infections, including tuberculosis, have occurred in patients treated with ruxolitinib. Before starting treatment, patients should be evaluated for active and latent infections and treatment with ruxolitinib delayed until active, serious infections have been resolved. During the study, investigators should carefully assess participants for signs and symptoms of infections and initiate appropriate treatment promptly. Progressive multifocal leukoencephalopathy has been reported with ruxolitinib treatment. Investigators should be alert to signs or symptoms and provide appropriate referrals or diagnostic measures. For additional information on ruxolitinib risks, see the Investigator's Brochure and commercial labeling information (ruxolitinib IB, Jakafi 2021, Jakavi 2022).

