4. STUDY DESIGN

4.1. Overall Design

This is a Phase 3, randomized, double-blind study of the combination of the PI3K δ inhibitor piasclisib or matching placebo and the JAK1/2 inhibitor ruxolitinib in participants with PMF or secondary MF (PPV-MF or PET-MF) with DIPSS risk category of intermediate or high. Prospective participants must have not received prior MF therapy with a JAK inhibitor or a PI3K inhibitor. After participants have been determined to be eligible for the study and completed the baseline symptom diary assessment for 7 days, they will be randomized to 1 of 2 treatment groups, with stratification for baseline platelet count ($\geq 100 \times 10^9/L$ vs 50 to $< 100 \times 10^9/L$ inclusive) and DIPSS risk category (high vs intermediate-2 vs intermediate-1). Note that if a participant's platelet count is $< 50 \times 10^9/L$ at baseline, the platelet count at screening will be used for stratification/randomization. Participants will receive study drug or matching placebo at a dose of 5 mg QD beginning on Day 1 and continuing for the duration of their participation in the study. Ruxolitinib dosing will also begin on Day 1, and dose level will be determined by baseline platelet count.

Figure 1 presents the study design schema, and Table 3, Table 4, and Table 5 present the SoA for study site visit assessments, post-crossover assessments, and laboratory assessments, respectively.

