8.1.3. Baseline

Participants who have signed the ICF and meet all of the inclusion criteria (see Section [5.1](#)) and none of the exclusion criteria (see Section [5.2](#)) may be enrolled in the study and will be contacted by clinical site staff to schedule the baseline visit. The baseline interval corresponds to the 7 days before initiating treatment with parsaclisib/matching placebo plus ruxolitinib and during which the baseline MRI (or CT scan in applicable participants) and symptom diary will be initiated.

- The MFSAF v4.0 diary should be distributed. Participants will be issued a handheld device and will complete the diary questions each night beginning on Day -7 up to the Week 24 visit.
- The MRI (or CT scan in applicable participants) should be conducted on the first or second day of the baseline interval to allow ample time for the laboratory to verify scan quality.
- To ensure per-protocol imaging completions, all MRI (or CT) scans for the study should be scheduled if possible to avoid missing scans at later timepoints in the study.
- Baseline laboratory samples should be collected within 3 days of projected Day 1 to avoid repeating on Day 1. Baseline platelet count values will be used for stratification/randomization. Note that platelet count at baseline for a participant with a screening value of $\geq 50 \times 10^9/L$ may have decreased below $50 \times 10^9/L$. For such participants, the screening value for platelet count will be used for stratification/randomization.

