1. INTRODUCTION

This is a Phase 3, randomized, double-blind study of the combination of the PI3K δ inhibitor parsaclisib or matching placebo and the JAK 1/2 inhibitor ruxolitinib in participants with PMF or secondary MF (PPV-MF or PET-MF) with DIPSS risk category of intermediate or high. Prospective participants must have not received prior MF therapy with a JAK inhibitor or a PI3K inhibitor. After participants have been determined to be eligible for the study and completed the baseline symptom diary assessment for 7 days, they will be randomized to 1 of 2 treatment groups, with stratification for baseline platelet count ($\geq 100 \times 10^9/L$ vs 50 to $< 100 \times 10^9/L$ inclusive) and DIPSS risk category (high vs intermediate-2 vs intermediate-1). If a participant's platelet count has decreased to $< 50 \times 10^9/L$ at baseline, the platelet count at screening will be used for stratification/randomization. Participants will receive study drug or matching placebo at a dose of 5 mg QD beginning on Day 1 and continuing for the duration of their participation in the study. Ruxolitinib dosing will also begin on Day 1, and dose level and protocol-allowed dose increases will be determined by baseline platelet count. Section 2 of the Protocol provides a detailed description of the investigational product, target patient population, rationale for doses to be examined, and potential risks and benefits of treatment with parsaclisib and ruxolitinib.

The purpose of this SAP is to provide details of the statistical analyses that have been outlined in the INCB 50465-313 Protocol.

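### Read literally, Table 10 footnote a starts ruxolitinib at 15 mg BID when platelets fall from ≥100 at screening to <50 at baseline, yet a smaller fall to 50 to <100 starts it at 5 mg BID

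*Protocol*

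**What the plan says.** All platelet counts here are × 10⁹/L.

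- **Starting dose.** Protocol Table 10 gives 5 mg BID for a baseline count of 50 to <100 and 15 mg BID for ≥100. Footnote a, whose marker is on the 5 mg entry, covers a count that has dropped below 50 by baseline: "the platelet count at screening should be used to determine the starting dose of ruxolitinib".
- **General dosing statements.** Protocol Section 1 (Treatment Groups and Duration) has participants receive "ruxolitinib, at doses determined by baseline platelet count, beginning on Day 1". Section 4.1 says "dose level will be determined by baseline platelet count", and SAP Section 1 says "dose level and protocol-allowed dose increases will be determined by baseline platelet count". Section 4.1 and SAP Section 1 mention the screening count only as the fallback for stratification and randomization.
- **Baseline counts below 50.** Section 8.1.3 foresees that a participant who screened at 50 or more may be below 50 at baseline, and says: "For such participants, the screening value for platelet count will be used for stratification/randomization".
- **Exclusion.** Exclusion 5a (Section 5.2) applies to counts below 50 "in the 4 weeks before screening or at the screening laboratory assessment". It does not name the baseline count.
- **Risk.** Section 2.6.2.1 states: "Dose-dependent, reversible thrombocytopenia has been observed in studies of participants with MF".

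**The concern.** A starting-dose rule based on platelets should not give a higher dose at a lower current count. If screening was 50 to <100, the footnote gives 5 mg BID, which is sensible. If screening was ≥100, it gives 15 mg BID to someone whose latest count is below 50. A participant with the same screening count and a milder fall gets 5 mg BID.

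For participants entering at 50 to <100, Section 6.7.1.3 makes 15 mg BID the absolute ceiling, reachable only by stepwise increases under platelet and neutrophil conditions. Footnote a, followed as written, starts a participant with a lower count at that ceiling on Day 1.

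The default toxicity rules do not readily correct this. Section 6.7.2 interrupts or reduces parsaclisib/placebo first and leaves ruxolitinib alone. Section 6.7.7 does not require a ruxolitinib change until 14 days of parsaclisib modification have brought no improvement, although the investigator may act sooner. In Table 11, the entry for platelets of 25 to <40 applies only if the grade has worsened from baseline.

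What is at stake is the safety of a very small number of participants, not the validity of the treatment comparison.

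**Working it through.** The plan states no figure to reproduce, so the check is to apply the rule as written.

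**Rule.** Reference count = screening count if baseline <50, otherwise baseline count. Starting dose = 15 mg BID if the reference count is ≥100, otherwise 5 mg BID. Screening below 50 is excluded (5a).

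**Starting dose (mg BID) by screening and baseline count:**

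| Screening | Baseline 30 | 49 | 50 | 75 | 99 | 100 | 120 |
|---|---|---|---|---|---|---|---|
| 60 | 5 | 5 | 5 | 5 | 5 | 15 | 15 |
| 99 | 5 | 5 | 5 | 5 | 5 | 15 | 15 |
| 100 | **15** | **15** | 5 | 5 | 5 | 15 | 15 |
| 120 | **15** | **15** | 5 | 5 | 5 | 15 | 15 |
| 200 | **15** | **15** | 5 | 5 | 5 | 15 | 15 |

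The reversal occurs only when screening is ≥100 and baseline is <50.

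**Dose difference.** 15 mg BID is 30 mg/day and 5 mg BID is 10 mg/day, so the ratio is 3. The first scheduled on-treatment hematology is at the end of Week 2 ± 3 days (Tables 3 and 5), that is Day 11 to 17. If no unscheduled count prompts an earlier change, the cumulative doses are:

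- Day 11: 11 × 30 = 330 mg versus 11 × 10 = 110 mg
- Day 14: 14 × 30 = 420 mg versus 14 × 10 = 140 mg
- Day 17: 17 × 30 = 510 mg versus 17 × 10 = 170 mg

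**Comparison with Section 6.7.1.3.** Increases of 5 mg/day, no more often than every 4 weeks from Week 4, give at the fastest 10 → 15 (Week 4) → 20 (Week 8) → 25 (Week 12) → 30 mg/day (Week 16). A participant entering at 50 to <100 therefore reaches 30 mg/day at Week 16 at the earliest.

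**How large and fast the fall must be.** From ≥100 to <50 is a fall of more than 50%; from 120 to 49 it is 71/120 = 59%. With screening on Day −35 to −8 (Table 3) and the baseline sample on Day −3 to −1, the interval is 8 − 3 = 5 days to 35 − 1 = 34 days, all before any study drug.

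**Frequency.** The documents give none. As an assumption for illustration only, 0 to 1% of 440 is 0 to 4 participants.

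**Limit on the anomaly.** Section 6.7.1.2 allows an increase above 15 mg BID only if the count has never been below 100 since baseline. That should stop this participant going higher, so the problem is confined to the starting dose.

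**Effect on the comparison.** Both counts precede randomization and the rule is the same in both arms, so it creates no bias between arms.

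**The case against.** **Placement of the marker.** It is on the 5 mg entry only, and a footnote normally qualifies the entry it is attached to. On that reading it covers only participants who screened at 50 to <100, and there is no anomaly. This may well be what was meant. But the footnote text carries no such limit, and Section 8.1.3 describes the affected group as anyone who screened at 50 or more, which includes those at ≥100.

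**Deliberate harmonization.** Amendment 1 (Appendix J, item 2) names Table 10 among the sections changed and gives as a reason the removal of discrepancies about which count to use. However, the change it describes concerns stratification and randomization. It does not justify a higher dose at a lower count, and the general dosing statements still point to the baseline count.

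**Section 2.5.2.** The same item lists Section 2.5.2 (Justification for Dose), which is not in the text available for this review. A rationale or limit there cannot be ruled out.

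**Investigator safeguards.** A sudden unexplained fall is something an investigator can act on. Exclusion 5 is open-ended, which Amendment 1 says is deliberate, and exclusion 19 allows exclusion on judgment. Table 3 marks "Inclusion/exclusion criteria" at screening, baseline and Day 1. Unscheduled counts (Section 4.1.1) and earlier ruxolitinib changes (Section 6.7.7) are permitted. These reduce the risk, but all rest on discretion and none changes the stated starting dose.

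**The right dose below 50.** Table 10 has no category below 50, so nothing visible establishes 5 mg BID as correct there. That is fair. The fix only extends the dose the footnote already gives to participants who screened at 50 to <100.

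**Conclusion.** The concern holds as a narrow patient-safety point. As written, footnote a assigns 30 mg/day instead of 10 mg/day when screening was ≥100 and baseline is below 50, while a smaller fall from the same screening count leads to the lower dose. This rests on the literal wording; the authors may have intended something narrower, and Section 2.5.2 could not be checked. The number affected is unknown, probably very low and possibly zero. The cumulative-dose figures assume that nobody reacts to the low count before Week 2. The trial's conclusions are not threatened: there is no efficacy bias and no meaningful effect on power. Confidence is medium, and the case for change is that it is cheap.

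**What to change.** Reword footnote a to say: *If the baseline platelet count is <50 × 10⁹/L, ruxolitinib starts at 5 mg BID regardless of the screening count.* Add a sentence to Section 6.7.1.3 that it governs later dose increases for these participants. Apply both only to participants randomized after the change, and align Section 2.5.2 if it repeats the dosing rule. Keep the screening-count fallback for stratification, and leave the SAP as it is.

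**Cost.** Two sentences, plus one IXRS check if IXRS assigns the ruxolitinib starting dose. No new test and no change to strata. Section 11.1 requires health-authority and IRB/IEC approval of amendments, so the change is best bundled with another one.

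**Downside.** A participant whose low baseline count is spurious or transient starts lower and escalates more slowly. A few participants may sit in the ≥100 stratum while starting at 5 mg BID; both are fixed before randomization, so this does not bias the comparison.
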